Diagnosis and main criteria for inclusion /exclusion	
Key inclusion criteria:
 
 • Men or women ≥ 18 years of age • T2DM as defined by the American Diabetes Association • Diagnosis of DKD with at least one of the following criteria at Run-in and Screening visits: 
 ○ persistent high albuminuria ¹ OR 
 ○ persistent very high albuminuria ². • Pretreated for at least 4 weeks prior to the Screening Visit with either ACEI or ARB at maximal tolerated labeled dose, preferably without adjustments to dose or choice of agent or other treatment • Serum potassium ≤ 4.8 mmol/L. 
Key exclusion criteria:
 
 • Confirmed significant non-diabetic renal disease, including clinically relevant renal artery stenosis • Uncontrolled arterial hypertension (ie, mean sitting SBP ≥ 170 mmHg, sitting DBP ≥ 110 mmHg at run-in visit, or mean sitting SBP ≥ 160 mmHg, sitting DBP ≥ 100 mmHg at screening) • Clinical diagnosis of chronic HFrEF and persistent symptoms (NYHA class II – IV) at Run-in visit (class 1A recommendation for MRAs) • Dialysis for acute renal failure within 12 weeks of Run-in visit • Renal allograft in place or scheduled kidney transplant within next 12 months • HbA1c $> 12\%$.
Study design	Randomized, double-blind, placebo-controlled, parallel-group, multicenter, event-driven

¹ **High albuminuria** (previously known as 'micro-albuminuria') is defined as 300 mg/g $>$ UACR ≥ 30 mg/g in 2 out of 3 first morning void samples.

² **Very high albuminuria** (previously known as 'macro-albuminuria') is defined as UACR ≥ 300 mg/g in 2 out of 3 first morning void samples.

Methodology	Randomized subjects will be treated with finerenone or placebo OD in a blinded fashion. The starting dose of study drug will depend on the subject's eGFR level at the Screening Visit: a lower dose of 10 mg OD if eGFR was between 25 to < 60 mL/min/1.73m ² , or the higher (target) dose of 20 mg OD if eGFR was ≥ 60 mL/min/1.73m ² . Study drug may be up-titrated from Visit 2 (Month 1) onwards provided potassium is ≤ 4.8 mmol/L and eGFR decrease is less than 30% below the value last measured. Down-titration or interruption of study drug is permitted at any time during the study for safety reasons.
Type of control	Placebo
Data Monitoring Committee	Yes
Number of subjects	Planned 12800 subjects screened, 6400 subjects randomized

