7.4 Dosage and administration - amended

This section was changed in Amendment 3, see Section 15.1.2.9.

As shown in Table 7–2, the starting dose of finerenone will depend on the eGFR value at the Screening Visit.

Thus, at randomization, subjects with an eGFR between 25 to < 60 mL/min/1.73m² at the Screening Visit (central laboratory results) will be assigned to the lower dose of finerenone

(10 mg) or placebo in addition to SoC, whilst subjects with an eGFR ≥ 60 mL/min/1.73m² will be assigned to the higher dose of finerenone (20 mg) or placebo in addition to SoC.

Table 7–2 Dosage of study drug for administration

eGFR value at the Screening Visit, based on central laboratory results:	25 to < 60 mL/min/1.73m ²		≥ 60 mL/min/1.73m ²	
Subject randomized to group: Receives	Finerenone 10 mg finerenone OD + SoC	Placebo Placebo OD + SoC	Finerenone 20 mg finerenone OD + SoC	Placebo Placebo OD + SoC
Study drug intake	One tablet of SD once daily, preferably in the morning at approximately the same time each day.			
Missed intake	
 • If >8 hours before the next scheduled dose, the subject should take one tablet of SD as soon as possible. • If ≤ 8 hours of the next scheduled dose, the subject should wait and take the next tablet of SD at the usual time. 			
Up-titration of dose Allowed from Visit 2 (Month 1) onwards provided that: 
 • Potassium is ≤ 4.8 mmol/L ^a • eGFR decrease is less than 30% below the value measured at the last scheduled visit ^a • Must be documented in eCRF 	20 mg finerenone OD, maintain SoC	Sham-titrate, maintain SoC	Not applicable	Not applicable
Down-titration of dose 
 • Only for safety reasons (for guidance, see Section 9.7.1) • Allowed any time during the study (e.g. between scheduled visits) • Must be documented in eCRF • An unscheduled safety visit is performed within an adequate timeframe proposed by the investigator 	
 • If at higher dose of SD, down-titrate to lower dose of SD, maintain SoC • If at lower dose of SD, interrupt SD, maintain SoC 			

Abbreviations: eGFR = estimated glomerular filtration rate; SD = study drug; SoC = standard of care

^a Potassium and eGFR according to local laboratory values

Intake of study drug

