Subjects will be instructed to take one tablet of study drug, preferably in the morning, at approximately the same time each day. The study drug can be taken with a glass of water, with or without food.

Missed intake of study drug

If the subject misses his/her scheduled daily intake of study drug, he/she should consider the following 2 options before continuing study drug intake:

- (1) If intake of the missed tablet is discovered >8 hours before the next scheduled dose, the subject should take the study drug as soon as possible
- (2) If the missed intake is discovered within 8 hours of the next scheduled dose, the subject should wait and take the next tablet at the usual time.

Up- and down-titration of study drug

The investigator is encouraged to up-titrate the dose of study drug at any time once the patient has been on a stable dose for 4 weeks (± 7 days) (e.g. from Visit 2 onwards for patient starting study drug on the lower dose) either at a regular visit or an Up-titration Visit. Up-titration can be performed provided:

- the potassium concentration (local laboratory value) is ≤ 4.8 mmol/L,

AND

- eGFR decrease (local laboratory value) is less than 30% below the value measured at the last regular visit.

Subjects who started with or were up-titrated to the target dose (20 mg OD) of the study drug but who do not tolerate this dose may be down-titrated at any point during the study, including between-scheduled visits if required for safety reasons. These subjects may be up-titrated again based on the rules provided above. If the subject is already at the lower dose, the study drug can be interrupted at the investigator's discretion (refer to Section 9.7.1 for guidance). If the study drug is interrupted for more than 7 days, the study drug should be re-started at the lower dose (10 mg OD).

Subsequent to an up-titration or re-start of study drug after interruption of study drug intake for more than 7 days, the investigator should perform an Up-titration Visit 4 weeks (± 7 days) after titration or restart, in order to monitor potassium levels and renal function (see Table 9-1). If a regular study visit will be scheduled to take place 4 weeks (± 7 days) after up-titration, the monitoring of potassium and renal function is assured and no Up-titration Visit has to be performed in addition. With down-titrations, the unscheduled safety visit may need a smaller time window and should be performed at the investigator's discretion.

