9.7 Other procedures and variables

9.7.1 Monitoring of blood potassium - *amended*

This section was changed in Amendment 3, see Section 15.1.2.31.

Hyperkalemia is a frequent event in subjects with DKD progressing to ESRD and one of the main risks identified from previous studies with MRAs including finerenone. Potassium will be monitored closely during this study, with assessments of potassium concentration scheduled at all visits (see [Table 9–1](#) for schedule).

During treatment with study drug, all assessments of potassium, including re-tests, will be performed at both local and central laboratories. Due to sample handling and extended transportation time to the central laboratory, falsely elevated serum potassium values in centrally (but not locally) analyzed samples have been observed in previous studies with finerenone. Since the value of potassium in the local sample is usually not affected by this and results from the local laboratory are available earlier, local samples will be taken not only for safety purposes but also for dose adjustments.

Re-checking of potassium values must be done at the latest within 72 hours of the investigator being aware of results that need confirmation. The investigator can perform a re-test at any time if they consider it necessary to confirm the potassium concentration of the local or the central sample.

Adjustment of dose after start of study drug intake based on blood potassium levels is provided in [Table 9–3](#).

Table 9–3 Blood potassium: guidance for dose adjustment at Visit 2 and subsequent visits

Blood potassium (mmol/L)	Action
First sample:	
≤4.8	If on lower dose of study drug, up-titrate to higher dose. If on higher dose of study drug, continue on the same dose.
4.9 to 5.5	Continue on the same dose.
>5.5	Withhold study drug and re-check potassium within 72 hours.
Second and subsequent samples:	
≤5.0	Re-start study drug at lower dose.
>5.0	Continue to withhold study drug; continue to monitor potassium and restart study drug at the lower dose only if potassium is ≤5.0

NOTE: lower dose = 10 mg once daily; higher dose = 20 mg once daily.

The following aspects have also to be taken into consideration:

- Blood potassium should be measured 4 weeks (\pm 7 days) after re-starting treatment or dose adjustment, especially after up-titration

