9.7.2.2 Local laboratory - amended

This section was changed in Amendment 3, see Section 15.1.2.32.

In addition to samples for the central laboratory, other blood **safety samples** will be taken from Visit 1 (Day 1; baseline) onwards (see [Table 9–1](#)) for analysis at the local laboratory. These samples may be obtained up to 72 hours before a scheduled visit.

The following *clinical chemistry* parameters must be measured for as long as subject is not prematurely discontinued from the study drug:

- Blood potassium
- Blood creatinine (eGFR will be calculated automatically in the eCRF using the CKD-EPI formula (36)).

Up-titration of the study drug will be based on local potassium and eGFR values and must be documented in the eCRF. Down-titration of the study drug will occur for safety reasons only (for guidance, see [Section 9.7.1](#) and [Table 7–2](#)).

Potassium values should be recorded using a single decimal point (e.g. 4.5 mmol/L or mEq/L). In the event of hyperkalemia, please see [Section 9.7.1](#) for guidance on treatment.

In women of childbearing potential, a **pregnancy test** will be performed locally, at the Screening Visit and following randomization at yearly visits as long as the subject is not permanently discontinued from the study drug (since more than 7 days). However, pregnancy tests in subjects of childbearing potential should be performed more frequently (e.g. at every visit) if this is required by national / institutional regulations. Both serological and urine tests are acceptable.

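### Table 9-3 directs up-titration on potassium alone and omits the eGFR condition that Section 7.4 requires

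*Protocol*

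**What the plan says.** Table 9-3 in Protocol Section 9.7.1 covers dose adjustment by blood potassium at Visit 2 and all later visits. In its row for potassium at or below 4.8 mmol/L the instruction is "If on lower dose of study drug, up-titrate to higher dose"; a patient already on the higher dose is to "continue on the same dose". The table note defines the doses as 10 mg and 20 mg. For repeat samples after a value above 5.5 mmol/L, once potassium is 5.0 mmol/L or lower, the instruction is "Re-start study drug at lower dose".

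The running text of Section 7.4 lets up-titration go ahead if local potassium is at or below 4.8 mmol/L and, joined by a capitalised AND, if the "eGFR decrease (local laboratory value) is less than 30% below the value measured at the last regular visit". The sentence before that list encourages investigators to up-titrate at any time "once the patient has been on a stable dose for 4 weeks", with a tolerance of 7 days either way. Table 7-2, in the same section, repeats the potassium limit and adds "eGFR decrease is less than 30% below the value measured at the last scheduled visit".

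Section 9.7.2.2 says: "Up-titration of the study drug will be based on local potassium and eGFR values and must be documented in the eCRF". Section 3.3 also names both measurements as the basis for up-titration. The Methodology entry of the synopsis requires that "eGFR decrease is less than 30% below the value last measured".

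**The concern.** Two parts of the protocol give different instructions for the same decision. Section 3.3 identifies hyperkalemia and worsening renal function as the main risks known from steroidal drugs of this class, and presents titration on potassium and eGFR as a way to limit them. The Table 9-3 row keeps the potassium half of that safeguard and drops the renal half. The action concerned doubles the dose, and the table applies throughout treatment, not only at the first titration.

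The cross-references run one way. Section 7.4 sends the investigator to Section 9.7.1 for down-titration, for interruption at the lower dose and for raised potassium. Nothing in Section 9.7.1 sends the reader back. A site that has followed a hyperkalemic patient into Table 9-3 can therefore reach the up-titration row without meeting the eGFR condition.

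**Working it through.** The plan gives no figure to reproduce here, so the check compares the texts and then applies them to assumed patients.

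**Conditions for up-titration, place by place**

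| Place in the protocol | Potassium (mmol/L) | eGFR | Time on stable dose |
|---|---|---|---|
| Synopsis, Methodology | at most 4.8 | fall under 30% from last measured value | not stated |
| Section 3.3 | named, no limit | named, no limit | not stated |
| Table 7-2 | at most 4.8 | fall under 30% from last scheduled visit | not stated |
| Section 7.4, text | at most 4.8 | fall under 30% from last regular visit | 4 weeks (± 7 days), in the encouragement sentence |
| Section 9.7.2.2 | named, no limit | named, no limit | not stated |
| Table 9-3 | at most 4.8 | **not stated** | not stated |

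Table 9-3 is the only one of the six without eGFR. Neither its note nor the bullets below it supply the condition. The bullets deal with re-measuring potassium, differences between central and local results, recurrent hyperkalemia, ECG and diet.

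**Can the two rules give different decisions?** Percentage fall = 100 × (1 − current eGFR / reference eGFR).

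Assumed patient on 10 mg: potassium 4.5, eGFR 50 at the last regular visit and 33 now.
- Fall = 100 × (1 − 33/50) = 34%.
- Table 9-3: potassium is at most 4.8, so go to 20 mg.
- Section 7.4: 34% is not under 30%, so up-titration is barred.

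**Where would the stable-dose wording matter, if it is a condition?**
- Shortest period it allows: 4 × 7 − 7 = 21 days.
- Earliest Visit 2: 30 − 7 = day 23.
- A patient who has stayed on the starting dose therefore already meets it at Visit 2.
- It can matter after a restart or down-titration. Assumed example: restart at 10 mg, then a regular visit 10 days later with potassium 4.7. Table 9-3 says 20 mg; on the strict reading, Section 7.4 says wait.

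**Synopsis comparator.** Local creatinine is also drawn at Up-titration Visits (Section 9.2.8), so the last measured value need not come from the last regular visit. Assumed eGFR at the last regular visit, at an Up-titration Visit in between, and now:
- 50, 40, 33: against the regular visit, 34% (barred); against the last value, 100 × (1 − 33/40) = 17.5% (allowed).
- 50, 60, 40: against the regular visit, 100 × (1 − 40/50) = 20% (allowed); against the last value, 100 × (1 − 40/60) = 33.3% (barred).

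The two wordings can differ in either direction, but only when an eGFR was measured between regular visits.

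**The case against.** The best defence is that Table 9-3 was never meant to be the up-titration rule. Its title calls it guidance on blood potassium, and its lead-in limits it to adjustment on potassium. The protocol refers to Section 9.7.1 for raised potassium, down-titration and interruption, while the up-titration row of Table 7-2 lists its own conditions. Sections 5 and 9.2.8 send sites to Section 7.4. Local creatinine is drawn with local potassium, and the eCRF calculates eGFR automatically. Titration is at the investigator's discretion, Section 8.1.1 allows dose reduction on creatinine or eGFR, and a check is due about four weeks after any up-titration. A wrong dose increase would require a site to overlook all of this.

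That argument stands as to practical weight: the intended rule can be recovered. It does not remove the contradiction, because the table does contain an up-titration instruction, that instruction is unconditional, and nothing there points to the missing condition.

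Three stronger readings are tempting, and the documents do not support them.

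- *The four weeks on a stable dose are a firm bar that Table 9-3 breaks.* The phrase sits in the sentence that encourages up-titration, outside the list of conditions, and Table 7-2 and the synopsis omit it too. Treating it as a condition is reasonable, but it is an interpretation. The first bullet under Table 9-3 also asks for a potassium measurement about four weeks after a restart or dose adjustment.
- *The synopsis sets a competing dosing rule.* It is a summary. Section 7.4 governs dosing, and its text and table agree in substance.
- *The inconsistency biases the treatment comparison or costs power.* The documents give no frequency of such dose increases. Titration is blinded, with sham titration on placebo, and nothing in the plan shows a route to bias.

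**Conclusion.** The inconsistency between Table 9-3 and Section 7.4 on eGFR is real and can be read directly from the current text. It is a minor internal inconsistency in a dosing-safety rule. Its consequence for an individual patient would be a move from 10 mg to 20 mg despite an eGFR fall that the dosing section treats as disqualifying. How often that could occur cannot be estimated from the documents, and the repeated statements of the eGFR condition make it unlikely. The patients above are assumed and show only that the rules can disagree.

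The conclusion on eGFR rests on taking Section 7.4 as the governing text, which the cross-reference in Section 5 supports. The stable-dose point depends on what the sponsor intended. The synopsis point is editorial.

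**What to change.** Keep the words "If on lower dose of study drug, up-titrate to higher dose" in the Table 9-3 row and add: provided the conditions in Section 7.4 are met, including an eGFR decrease of less than 30% versus the last regular visit.

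Decide whether four weeks (± 7 days) on a stable dose is a condition or only encouragement. If it is a condition, state it in both Table 7-2 and Table 9-3; correcting only one would leave the same gap in the other.

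As an editorial change, make the synopsis compare eGFR with the last regular visit. Using one term for that visit in both Table 7-2 and the Section 7.4 text would be a further optional tidy-up.

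The drafting cost is one clause and one synopsis phrase, plus a line in each table if the stable-dose condition is confirmed. Design, data collection and analysis do not change. The administrative cost is larger: Section 13.1 requires investigator signature and the external approvals at each center before an amendment takes effect there, and Section 5 plans about 900 centers. The change does not justify an amendment of its own and should go into the next one issued for other reasons. The documents mention no such amendment: the SAP of 15 February 2021 still rests on the protocol version of 12 March 2019.

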9.7.2 Laboratory assessments

9.7.2.1 Central laboratory

The name and the address for the central laboratory service provider can be found in the documentation supplied by the vendor. Only centrally analyzed blood samples will be considered for statistical analysis, unless otherwise specified. Details of the collections, shipment of samples and reporting of results by the central laboratory will be provided to the investigators in the Laboratory Manual.

Laboratory evaluations (*hematology, HbA_{1c}, clinical chemistry and urinalysis* parameters) are shown in [Table 9–4](#). Hematology, HbA_{1c} and (full) clinical chemistry are considered as ‘*Full central laboratory*’ assessments.

Laboratory evaluations will be performed according to the visit schedule (see [Table 9–1](#)).

Table 9–4 Central laboratory parameters

Parameter	Component
Hematology	White blood cell count (WBC), red blood cell count (RBC), hemoglobin, hematocrit, mean corpuscular volume (MCV), mean corpuscular hemoglobin (MCH), MCH concentration (MCHC), platelets
Glycated hemoglobin (HbA1c)	HbA1c only
Clinical chemistry (full)	Aspartate aminotransferase (AST), alanine aminotransferase (ALT), alkaline phosphatase (AP), gamma glutamyl transpeptidase (GGT), lactate dehydrogenase (LDH), creatine kinase (CK), cholesterol (high density lipoprotein [HDL], low density lipoprotein [LDL], total), triglycerides, creatinine, eGFR (CKD-EPI), blood urea nitrogen, uric acid, bilirubin, sodium, serum potassium, magnesium, total protein, albumin, high-sensitivity C-reactive protein (hs-CRP)
Clinical chemistry (limited)	Serum creatinine, eGFR (CKD-EPI), sodium, serum potassium
Urinalysis	Urine albumin-to-creatinine ratio (UACR) will be measured in the first morning void urine samples collected at the subject's home on 3 consecutive days

9.7.2.2 Local laboratory - amended

This section was changed in Amendment 3, see Section 15.1.2.32.

In addition to samples for the central laboratory, other blood **safety samples** will be taken from Visit 1 (Day 1; baseline) onwards (see [Table 9–1](#)) for analysis at the local laboratory. These samples may be obtained up to 72 hours before a scheduled visit.

The following *clinical chemistry* parameters must be measured for as long as subject is not prematurely discontinued from the study drug:

- Blood potassium
- Blood creatinine (eGFR will be calculated automatically in the eCRF using the CKD-EPI formula (36)).

Up-titration of the study drug will be based on local potassium and eGFR values and must be documented in the eCRF. Down-titration of the study drug will occur for safety reasons only (for guidance, see [Section 9.7.1](#) and [Table 7–2](#)).

Potassium values should be recorded using a single decimal point (e.g. 4.5 mmol/L or mEq/L). In the event of hyperkalemia, please see [Section 9.7.1](#) for guidance on treatment.

In women of childbearing potential, a **pregnancy test** will be performed locally, at the Screening Visit and following randomization at yearly visits as long as the subject is not permanently discontinued from the study drug (since more than 7 days). However, pregnancy tests in subjects of childbearing potential should be performed more frequently (e.g. at every visit) if this is required by national / institutional regulations. Both serological and urine tests are acceptable.

9.7.3 Physical examination

Abnormal physical examination findings are recorded either as medical history or as an AE (see Section 9.6.1.1).

A complete physical examination will be performed at the Run-In and Screening Visits, at the yearly visits and again at the PD and EOS Visits (see Table 9–1).

9.7.4 Weight, height, hip and waist circumference

Body weight (to the nearest 0.1 kg in indoor clothing without shoes) will be measured at all scheduled visits except the PT Visit (see Table 9–1). Height as well as hip and waist circumference in centimeters will be only measured at the Run-in Visit.

9.7.5 Measurement of vital signs

Vital signs will be assessed at all scheduled visits except the PT Visit (see Table 9–1). This will include blood pressure (BP) and pulse measurements.

BP will be measured by using a standard sphygmomanometer with an appropriate size cuff in the sitting position after 5 minutes of rest.

There must be 3 consecutive BP readings with at least a 1-minute interval between each reading (all 3 readings should be obtained within a maximum of 20 minutes).

The same arm and the appropriate size cuff should be used for measurements at each visit.

